1.6.4 Ultrasound-Accelerated Thrombolysis

After demonstrating the possibilities of more effective thrombolysis using ultrasound to accelerate the process, catheter-directed, ultrasound-accelerated thrombolysis (UAT) was studied for submassive and massive PE. Two multicenter, prospective studies were completed, ULTIMA and SEATTLE-II. ULTIMA was a randomized analysis of UAT vs. anticoagulation alone in 59 subjects with submassive PE.⁴⁷ UAT was more effective than anticoagulation in normalizing RV function. No intracranial bleeding was observed. The SEATTLE-II trial evaluated differing doses of rt-PA PAT infused over varying timeframes in 150 subjects with submassive and massive PE.⁴⁸ These studies concluded that catheter-directed pulmonary artery thrombolysis with rt-PA was safe and effective in the treatment of submassive (intermediate-risk) PE, at least with respect to reductions in RV/LV ratio without intracranial hemorrhage. This conclusion, however, has not been without controversy. A 2017 review of 23 studies and 700 subjects found no difference in the rate of bleeding complications between UAT and standard, catheter-directed thrombolysis, 12% with UAT vs. 10% with standard catheter-directed thrombolysis.²¹ The review, however, documented a trend toward improved survival with UAT; 4% vs. 9% in the UAT and standard thrombolytic subjects, respectively.

1.6.5 Percutaneous Pulmonary Artery Thromboembolectomy

Interest in percutaneous pulmonary artery thromboembolectomy flourished on a clinical landscape of effective but relatively slow thrombolytic treatment of PE and risk of thrombolytic-related bleeding complications even when drugs were administered with a lower-dose, catheter-directed approach. Direct pulmonary arterial thromboembolectomy offered the opportunity for rapid removal of thrombus while limiting hemorrhagic, thrombolytic-related complications in those cases where thrombectomy could be utilized as a sole therapy, without pharmacologic thrombolysis.

Historically, percutaneous thromboembolectomy for PE predated catheter-directed thrombolysis. The therapy began with the Greenfield suction catheter, first reported in 1969.⁴⁹ After that, other technologies were attempted, including fragmentation of proximal emboli,^{50,51} rheolytic thrombectomy,⁵²⁻⁵⁶ and the use of various pulmonary artery thromboembolectomy devices.⁵⁷⁻⁵⁹ To the extent that the percutaneous thromboembolectomy devices removed obstructing thromboembolism without the need for thrombolytic therapy, such devices presented the potential for normalization of pulmonary arterial flow without the hemorrhagic complications associated with thrombolytic agents.

2 STUDY DEVICE

2.1 OVERVIEW

The FlowTriever Retrieval/Aspiration System is a single-use over-the-wire catheter-based system for the minimally invasive treatment of thromboemboli in the peripheral vasculature and the treatment of pulmonary embolism. The device was cleared in the US under 510(k) number K180466, May 17, 2018, and CE Mark on December 30, 2020. The FlowTriever System is a Class II device in the US and a Class III device in Europe, intended for use in the peripheral vasculature and for the treatment of pulmonary embolism.

2.3 INDICATIONS FOR USE

The FlowTriever Retrieval/Aspiration System is a single-use over-the-wire catheter-based system for the minimally invasive treatment of thromboemboli in the peripheral vasculature and the treatment of pulmonary embolism. The FlowTriever System is indicated for the non-surgical removal of emboli and thrombi from blood vessels; the injection, infusion, and/or aspiration of contrast media and other fluids into or from a blood vessel. The completion of the FLARE prospective clinical trial resulted in FDA clearance and CE Mark for the treatment of pulmonary embolism.

3 PRIOR INVESTIGATIONS

The FlowTriever System was evaluated in a US pivotal Investigational Device Exemption trial, the FlowTriever Clinical Embolectomy Clinical Study (FLARE) study, in subjects with submassive (i.e., intermediate-risk) PE. The study was a prospective, multicenter study to evaluate the safety and effectiveness of the FlowTriever System in subjects eligible for endovascular treatment of acute PE.

3.1 DESIGN OF THE FLARE STUDY

A maximum of 20 study sites were planned to participate in the study, and no single study site could enroll more than 25% of the total subjects. The study population comprised 106 subjects with acute submassive PE.

Primary safety and primary effectiveness performance goals (PG) were used in the study. For the safety PG, the results from seven studies with acute PE patients treated with a heparin control arm were used to develop a composite MAE rate. MAEs were defined when one or more of the following occurred within 48 hours: Device-related mortality, major bleeding, treatment-related clinical deterioration, treatment-related pulmonary vascular injury, or treatment-related cardiac injury. Combining these composite MAE rates yielded an estimate of 16% with a 95% confidence interval of 6.7% to 25.8% after adjusting for heterogeneity among studies. The PG was chosen as the upper 95% confidence limit rounded down to two digits, for a safety PG of 25%.

The primary effectiveness performance goal was the change in RV/LV ratio from baseline to 48 hours. The PG was based on heparin-treated subjects from four studies in which heparin was a control to an active pharmaceutical drug. Combining these results in a meta-analysis yielded a mean change from baseline of 12% with 95% confidence limits of 4% to 21% after adjusting for heterogeneity among studies, for an effectiveness PG of 12%.

Subjects were followed for 30 days post-procedure with CTPA at 48 hours and assessment of AEs through 30 days. The primary safety endpoint was assessed from the 48-hour MAE rate and the primary effectiveness endpoint from the change between the baseline and 48-hour CTPA imaging studies.

[figure not shown]
The sample size for effectiveness was computed based on an estimated RV/LV ratio change from baseline. For 80% power to detect an RV/LV ratio greater than 0.12 using a one-sided alpha = 0.025, the sample size needs to be at least 62, 38, or 26 assuming a true RV/LV ratio of 0.20, 0.225 or 0.25, respectively.

The sample size for safety was based on the PG of 25% for the composite endpoint. The true composite endpoint rate for the FlowTriever was expected to be about 13%, according to data from the historical studies used for the PG estimation. Additionally, rates of 15% and 17% were considered. For 80% power to detect a difference from the expected lower composite endpoint rates of 13%, 15%, and 17% compared to the performance goal with a one-sided alpha = 0.05, 70, 103, and 167 subjects would be needed if the true rates were 13%, 15%, and 17%, respectively. Since a conservative sample size for safety was calculated to be 103, 103 was used as the sample size for this study, not adjusted for subjects receiving thrombolytics. It was assumed that approximately 15% of the subjects would receive thrombolytics so that $103/0.85=121.2$ or up to 122 subjects could be enrolled.

3.2 STUDY RESULTS

The disposition of subjects in the FLARE trial is depicted in **Figure 3**. In all, 106 subjects were enrolled and treated with the study device; 104 without thrombolytics. Among these, 101 had evaluable CTPA studies suitable for the primary effectiveness endpoint. There were also 101 subjects that had 48-hour data suitable for the primary safety endpoint. The mean baseline RV/LV ratio was 1.5 ± 0.4 , and the mean 48-hour RV/LV ratio was 1.2 ± 0.3 . Three subjects had missing values for the primary effectiveness endpoint at the 48-hour visit resulting in 101 subjects with both a pre-and post- RV/LV ratio for comparison. For these paired subjects, the mean change (reduction) in RV/LV ratio from pre- to post- was 0.38 ± 0.3 , with a range from an increase of 0.4 to a decrease of 1.4. This mean change in RV/LV ratio was 0.38 and the p-value < 0.0001, indicating that the null hypothesis was rejected and the FlowTriever device met the performance goal.^a

Figure 3. Disposition of Subjects in the FLARE Trial

*Subject who did not meet eligibility requirement died during follow-up period.

^a The p-value is from a one-sided t-test (Wald statistic) from the multiple imputation analysis, testing the null hypothesis that the mean change is not greater than the performance goal of 0.12.

For the primary safety endpoint, 4 subjects (3.8%) in the mITT population experienced one or more MAEs. The composite endpoint of 3.8% was statistically lower than the performance goal of 25% (p-value <0.0001), with an upper one-sided 95% confidence limit of 8.6%. The upper one-sided 95% confidence limit for the ITT population was 8.4%, which was significantly less than the performance goal of 25%.

In sum, the FLARE trial met its primary safety and effectiveness endpoints. This trial was the basis for the US FDA 510(k) clearance of the device in May 2018.

4 STUDY OBJECTIVE

The primary study objective is to evaluate the safety and effectiveness of the FlowTriever System for use in the removal of emboli from the pulmonary arteries in the treatment of acute pulmonary embolism (PE). The use of the device will be assessed in a real-world population, with eligibility criteria that closely approximate its use in clinical practice.

5 OUTCOME VARIABLES

5.1 PRIMARY SAFETY ENDPOINT DEFINITION

The primary safety endpoint is the rate of Major Adverse Events (MAE). MAEs are defined as a composite when one or more of the following events occur:

- Device-related mortality through 48 hours after the index procedure, or
- Major bleeding through 48 hours after the index procedure, or
- Intraprocedural device- or procedure-related adverse events, including:
 - Clinical deterioration defined by hemodynamic or respiratory worsening, or
 - Device-related pulmonary vascular injury, or
 - Device-related cardiac injury

The components of the composite MAE endpoint will be assessed by the independent Medical Monitor.

5.2 SECONDARY ENDPOINTS

The secondary endpoints of the study will assess safety, effectiveness, and utility measures, as follows.

5.2.1 Secondary Safety Endpoints

- Individual components of the MAE composite endpoint
- Major access site complications requiring open surgical or endovascular intervention or blood transfusion
- All-cause mortality within 30 days
- Device-related serious adverse events within 30 days

5.2.2 Secondary Effectiveness Endpoint

- Reduction in pulmonary artery pressures during the procedure
- Hemodynamic improvements during the procedure, including cardiac index (CI) and stroke volume index (SVI), right ventricular stroke work index (RVSWI), pulmonary artery pulsatility index (PAPi), and total pulmonary vascular resistance (TPVR)^b
- Reduction in right-ventricular/left-ventricular (RV/LV) ratio from baseline to 30 days and 6 months; as measured by echocardiography

5.2.3 Utility Measures

- Fluoroscopy time
- Contrast used
- Estimated blood loss during the index procedure
- Thrombectomy Time
- Length of intensive care unit stay, if any
- Length of total hospital stay

6 STUDY DESIGN

The FLASH Registry study is a prospective, single-arm, multicenter analysis of the FlowTriever System for intermediate-risk (submassive) and high-risk (massive) PE. The Registry will collect data on demographics, comorbidities, details from the PE diagnosis and treatment, and clinical outcomes through 6-month follow-up.

Up to 1000 patients (up to 800 US, up to 200 Europe) with PE will be enrolled at up to 100 (up to 70 US, up to 30 Europe) Registry sites. All patients who sign consent and are treated with the FlowTriever System will comprise the analytic dataset.

Conservative Therapy Sub-study: (US Patients Only) Up to 300 additional patients with anticoagulation treatment as the initial planned primary treatment strategy for intermediate risk PE will be evaluated. Clinical assessments will be performed at Baseline, 48 hours, 30 days, and 6 months.

Conservative Therapy Sub-study: (US Patients Only) Approximately 150 of these patients should be considered intermediate-high risk. Enrollment will be limited to 60 patients per site. The Conservative Therapy Sub-study will

^b The Fick Method will be utilized to estimate cardiac output. Measurement of pulmonary artery oxygen saturation, peripheral arterial oxygen saturation by pulse oximetry or arterial line, and the hemoglobin concentration is required. Body surface area (BSA) will be approximated with the modified DuBois formula; $BSA = 0.007184 \times (\text{height in cm})^{0.725} \times (\text{weight in kg})^{0.425}$. O₂ consumption is approximated as body weight in kg \times 3 ml/kg.

Cardiac output (CO) is estimated as the O₂ consumption divided by the product of arterial-mixed venous O₂ difference, hemoglobin concentration, and the constant 13.6. As an example, an 80 kg patient with a hemoglobin of 11 g/dL, a mixed venous (pulmonary artery) O₂ saturation of 60% and an arterial O₂ saturation of 97% would have an estimated cardiac output of $(80 \text{ kg} \times 3 \text{ ml/kg}) / [(0.97 - 0.60) \times 13.6 \times 11 \text{ g/dL}]$, or 210/ 53, or 4.34 L/min. If the BSA is 1.7, the cardiac index is 4.34/1.7, or 2.6. If the heart rate is 80, the SVI is 2,600 / 80 or 32.5 ml.

RVSWI is calculated as the (mean pulmonary artery pressure – right atrial pressure) \times stroke volume index \times 0.136.

PAPi is calculated as (pulmonary artery systolic – pulmonary artery diastolic) / right atrial pressure.

TPVR is calculated as the mean pulmonary artery pressure / cardiac output.

collect data on demographics, comorbidities, details from the PE diagnosis and treatment, and clinical outcomes through 6-month follow-up.

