Asymptomatic PE	Pulmonary embolism detected on an imaging study in a patient without clinical symptoms.
CTED/Post PE Syndrome	Chronic thromboembolic Disease: Per 2019 ESC Guidelines, some patients may present with normal pulmonary hemodynamics at rest despite symptomatic disease. If other causes of exercise limitation are excluded, these patients are considered as having chronic thromboembolic disease (CTED). From Respiratory medicine journal on PE, (CTED) is characterized by similar symptoms and imaging findings to CTEPH but without pulmonary hypertension at rest.

CTEPH	Chronic thromboembolic pulmonary hypertension: Per 2019 ESC Guidelines, CTEPH is a disease caused by the persistent obstruction of pulmonary arteries by organized thrombi, leading to flow redistribution and secondary remodeling of the pulmonary microvascular bed. The diagnosis of CTEPH is based on findings obtained after at least 3 months of effective anticoagulation, to distinguish this condition from acute PE. The diagnosis requires a mean PAP of ≥ 25 mmHg along with a pulmonary arterial wedge pressure of ≤ 15 mmHg, documented at right heart catheterization in a patient with mismatched perfusion defects on V/Q lung scan.
High-Risk PE	Per ESC guidelines 2019: High-Risk PE determined by hemodynamic instability, PESI III-V or sPESI ≥ 1 , RV Dysfunction, and Elevated cardiac troponins. Note Definition of hemodynamic instability, which delineates acute high-risk pulmonary embolism (one of the following clinical manifestations at presentation). 1. Cardiac Arrest: Need for cardiopulmonary resuscitation, 2. Obstructive Shock: Systolic BP < 90 mmHg or vasopressors required to achieve a BP > 90 mmHg despite adequate filling status AND End-organ hypoperfusion (altered mental status; cold, clammy skin; oliguria/anuria; increased serum lactate), OR 3. Persistent Hypotension: Systolic BP < 90 mmHg or systolic BP drop > 40 mmHg, lasting longer than 15 min and not caused by new-onset arrhythmia, hypovolemia, or sepsis
Intermediate High-Risk PE	Per ESC guidelines 2019: Intermediate High-Risk PE determined by no hemodynamic instability, PESI III-V or sPESI ≥ 1 , RV Dysfunction, and Elevated cardiac troponins
Intermediate Low-Risk PE	Per ESC guidelines 2019: Intermediate Low-Risk PE determined by no hemodynamic instability, PESI III-V or sPESI ≥ 1 , and 1 or none of the following: RV Dysfunction; Elevated cardiac troponins.
Patient/ Subject	Participants in the study.

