2.2.2. Secondary Effectiveness Endpoints

- Reduction in pulmonary artery pressures during the procedure
- Hemodynamic improvements during the procedure, including cardiac index (CI) and stroke volume index (SVI), right ventricular stroke work index (RVSWI), pulmonary artery pulsatility index (PAPI) and total pulmonary vascular resistance (TPVR)
- Reduction in right-ventricular/left-ventricular (RV/LV) ratio from baseline to 48 hours, 1 month, and 6 months; as measured by CT or echocardiography

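### The RVSWI formula multiplies by 0.136 where mmHg × mL converts to g·m by 0.0136, so a secondary effectiveness endpoint computed as written is ten times too large

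*Protocol*

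**What the plan says.** Protocol Section 5.2.2 lists RVSWI among the hemodynamic secondary effectiveness endpoints: "right ventricular stroke work index (RVSWI), pulmonary artery pulsatility index (PAPi), and total pulmonary vascular resistance (TPVR". SAP Section 2.2.2 lists it too ("right ventricular stroke work index (RVSWI), pulmonary artery pulsatility index (PAPI) and total pulmonary vascular resistance (TPVR") but gives no formula.

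The only definition is in Protocol footnote b, attached to Section 5.2.2 and printed under Section 6: "RVSWI is calculated as the (mean pulmonary artery pressure – right atrial pressure) \times stroke volume index \times 0.136". It gives no unit for the pressures or for the result, and no worked RVSWI value. The same footnote does work through cardiac output, cardiac index and stroke volume index, and ends with "If the heart rate is 80, the SVI is 2,600 / 80 or 32.5 ml". SVI therefore enters the formula in mL. The pressure unit has to be taken from elsewhere. Protocol Section 15 gives mean pulmonary artery pressure in mmHg ("The diagnosis requires a mean PAP of ≥ 25 mmHg"), and every other pressure in the documents that carries a unit is also in mmHg.

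Protocol Section 10.2 and SAP Section 5.2 plan descriptive summaries (mean, median, quartiles, minimum, maximum). The SAP also allows crude p-values, with the Wilcoxon signed-rank test for paired continuous outcomes.

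**The concern.** A pressure times a volume is work, and turning mmHg × mL into g·m needs a fixed physical constant. That constant has the digits 136, but the printed value is a factor of ten away from it, which suggests a misplaced decimal point.

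The study is descriptive, so its results for this endpoint are the absolute RVSWI values before and after the procedure and the change between them. A wrong multiplier affects every one of them, and they could not be set beside RVSWI values reported elsewhere in g·m/m². The planned test would give no warning, because multiplying both members of each pair by the same constant leaves the ranks and signs of the differences unchanged.

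**Working it through.** **Inputs**

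- Multiplier: 0.136 (Protocol footnote b).
- SVI: 32.5 mL per m² of body surface (footnote b, which writes the unit only as ml).
- Pressure unit: mmHg (Protocol Section 15; footnote b is silent).
- RVSWI unit: not stated. Assumed g·m/m² per beat; other readings are tried below.
- Mean pulmonary artery (mPAP) and right atrial (RAP) pressures: not given for any example patient. Assumed, with a range.

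**Step 1: reproduce the footnote's own chain up to SVI**

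- O₂ consumption: 80 × 3 = 240 mL/min.
- Denominator: (0.97 − 0.60) × 13.6 × 11 = 55.35.
- Cardiac output: 240 / 55.35 = 4.34 L/min, as stated.
- Cardiac index: 4.34 / 1.7 = 2.55, stated as 2.6.
- SVI: 2,600 / 80 = 32.5 mL, as stated.

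The end figures reproduce, so SVI is in mL. The printed intermediate step does not: the footnote has "or 210/ 53, or 4.34 L/min", but 210 / 53 = 3.96. The stated inputs give 240 / 55.4. The 13.6 in this step belongs to the oxygen-content calculation and is separate from the RVSWI constant.

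**Step 2: derive the RVSWI constant**

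- From the density of mercury: 1 mmHg × 1 mL = 13.6 g/cm³ × 0.1 cm × 1 cm³ = 1.36 g·cm = 0.0136 g·m.
- From SI units: 133.322 Pa × 10⁻⁶ m³ = 1.33322 × 10⁻⁴ J. One g·m is 9.80665 × 10⁻³ J, so this is 0.013595 g·m.
- Ratio of the printed constant to the derived one: 0.136 / 0.013595 = 10.00.

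**Step 3: look for units that would make 0.136 right**

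| Pressure × volume | Result unit | Correct factor | 0.136 as a multiple of it |
|---|---|---|---|
| mmHg × mL | g·m | 0.0136 | 10.0 |
| mmHg × mL | mJ | 0.1333 | 1.02 |
| kPa × mL | g·m | 0.102 | 1.33 |
| cmH₂O × mL | g·m | 0.0100 | 13.6 |
| cmHg × mL | g·m | 0.136 | 1.0 |

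Only centimetres of mercury fit, and no pressure in either document is in that unit.

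**Step 4: size, with the footnote's SVI of 32.5**

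| Assumed mPAP / RAP (mmHg) | As written (× 0.136) | With 0.0136 (g·m/m²) |
|---|---|---|
| 33 / 10 | 23 × 32.5 × 0.136 = 101.7 | 10.2 |
| 30 / 10 | 20 × 32.5 × 0.136 = 88.4 | 8.84 |
| 25 / 8 | 17 × 32.5 × 0.136 = 75.1 | 7.5 |

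Over assumed mPAP of 20 to 40 and RAP of 5 to 15 mmHg, the formula gives 22.1 to 154.7 as written and 2.2 to 15.5 with 0.0136.

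**Step 5: would the planned test show it?** In 60 simulated pairs, the Wilcoxon signed-rank p-value was 0.00916 both before and after multiplying all values by ten. Percent change is unaffected for the same reason.

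**The case against.** The strongest reply is that the tenfold figure is conditional. Neither document states a unit for RVSWI, and footnote b gives none for pressure. If millijoules were meant, 0.136 would be only about 2% high. That condition is real and must be stated. It does not rescue the formula: with mmHg and mL the constant is exact for neither unit, and its digits are those of the g·m conversion. On the kindest reading, the plan still needs a stated unit and a different constant.

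A second point is that the documents contain no eCRF specification, code or output, so they do not show that 0.136 is what was programmed. The footnote itself prints a wrong intermediate step yet reaches the right cardiac output. This stands as a limit on what can be said about actual results. It does not change what follows if the plan is applied as written.

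Third, the consequence is bounded. A constant multiplier can be undone by dividing by ten, and direction, percent change and any signed-rank p-value are correct. RVSWI is one of five hemodynamic indices in one secondary bullet of a study without formal hypotheses. The primary endpoint, pulmonary artery pressures, CI, SVI, PAPi, TPVR and RV/LV ratio do not use this constant. All of that is true. But a reader can undo the factor only after noticing it, and in a descriptive study the absolute values are the result.

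Finally, the 210/53 slip feeds no endpoint and is clerical. It adds no weight to the main point.

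**Conclusion.** The formula is wrong as written. For pressure in mmHg, SVI in mL/m² and RVSWI in g·m/m², every pre-procedure value, post-procedure value and absolute change comes out exactly ten times too large, for every patient. The pressure unit is inferred from the rest of the protocol. The unit of the result is an assumption, though the alternative of millijoules does not make 0.136 correct either. Because footnote b is the sole definition of this endpoint in either document, following the plan gives wrong reported values. Whether the error has reached the code or any output cannot be judged from the documents.

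**What to change.** - In Protocol footnote b, replace 0.136 with 0.0136. State that pressures are in mmHg, SVI in mL/m² and RVSWI in g·m/m² per beat.
- Repeat the corrected formula and units in SAP Section 2.2.2, so that the analysis does not depend on a protocol footnote.
- Check any eCRF derivation and the analysis code for the constant. If 0.136 was used, rerun any RVSWI output that exists.
- While editing the footnote, correct the intermediate step of the cardiac output example to 240/55.4. The final 4.34 L/min stays as it is.

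The cost is one constant and its units in the protocol, one line in the SAP, a code check and, if needed, a rerun of the RVSWI tables. No new data are required.
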